3.5.4 Consent Procedures

The consent letter will be presented to each patient while in the post-partum unit. The nature of the study will be explained to the patient and they will be given sufficient time to read the letter and pose any questions they may have. The subject will be asked if they are agreeable to completing the survey. A written consent from the subject will not be obtained.

3.5.5 Subject Costs and Compensation

There are no costs or compensation associated with participation in the study.

3.6 Chart Review Selection

Not applicable

4. Study Variables

4.1 Independent Variables or Interventions

RUTGERS APPROVED

THE STATE UNIVERSITY
Protocol Version 1.0 - 04/21/15
IRB ID: Pro20150001531
Approval Date: 4/30/2015
Expiration Date:

Add protocol title
PI name

Not applicable

4.1.1 Drug or Device Interventions

Not applicable

4.2 Dependent Variables or Outcome Measures

Study instruments are as follows:

Labor Pain Control Pamphlet –English and Spanish

We will provide information of available labor analgesia options (epidural, combined spinal/epidural, spinal, remifentanyl patient-controlled analgesia, and intravenous opioids) to expecting mothers. Using a pamphlet written in English or Spanish disseminated to pregnant women in clinic or in the labor and delivery unit, the procedures and their risks and benefits will be explained in simple terms.

Questionnaire- English and Spanish

After delivery, patients will be asked to complete a questionnaire addressing their thoughts about the pamphlets and their overall satisfaction with their labor analgesia. Our analysis will focus on the utility and effect of education materials on maternal informed consent for labor analgesia, on maternal choice of analgesia modality, and on maternal anxiety regarding their labor analgesia plan.

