1.1 Objectives

The study objectives are as follows:

1. To educate patients as to the various options available to them for labor analgesia.
2. To determine if the education material provided is helpful to patients in choosing a preference for a particular analgesia modality.
3. To determine if the education provided is helpful in reducing maternal anxiety.

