1.2 Hypotheses

The hypothesis is that providing written material regarding labor analgesia options will improve maternal satisfaction and lessen anxiety in regard to labor.

2. Background and Significance

Background

Many analgesic options exist for laboring parturients, but labor may not be the best time to start informing patients of their options. Many patients begin the labor process with a plan in place for their analgesia. Unfortunately, internet resources regarding labor analgesia that are available to the lay parturient are poor and often lead to misconceptions about the options and their risks. A significant number of patients refuse neuraxial analgesia based on misunderstandings, concerns about the procedure, or a lack of faith in the provider. Some women want a “natural childbirth” and/or control over their labor experience. Forty-seven percent of minority women feel inadequately educated about anesthesia, are less likely to trust physicians, and are less likely to receive epidurals. However, greater than 10% of obese women changed their preference toward epidural analgesia following antenatal consultation. Also, 50% of patients planning for analgesia-free labor request neuraxial analgesia after experiencing labor pain.³

Additionally, the question exists as to the quality of informed consent from a patient undergoing contraction pain and possible sedation from analgesic medications. The

RUTGERS APPROVED

THE STATE UNIVERSITY OF NEW JERSEY

Protocol Version: 20150001/531

Approval Date: 4/30/2015

Expiration Date:

Add protocol title
PI name

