3.1. Duration of Study

The study will commence upon receipt of the written educational material in the subject's preferred language. The material will provide a second time upon arrival to the Labor and Delivery Suite and at that time a discussion will be held with the anesthesia care provider regarding the options and their risks and benefits for analgesia and anesthesia for labor and delivery (15-20 minutes). The study will end following delivery when the subject completes the survey on the post-partum unit on F Green. The survey is expected to take 10-15 minutes.

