3.5.1 Inclusion Criteria

1. Postpartum women ages 18 and older
2. Patients who speak and read English or Spanish
3. Patients who received our informational pamphlet while pregnant or in labor
4. Patients who are able to consent and make medical decisions
5. Patients undergoing labor or trial of labor after cesarean delivery
6. Patients who undergo cesarean delivery after trial of labor

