4.4 Potential for Benefit

The potential benefit maybe that the subject is less anxious about the labor and delivery experience. The information gleaned from this data will be helpful to the investigators in regard to determining the needs of the patient population that is served.

5. Data Handling and Statistical Analysis

The paper survey will be inputted to an excel spread sheet in a password protected computer. This computer is located in the research office in the anesthesiology department. This data will only be accessible to members of the study team. The survey is anonymous. No link to the personal health identifiers and data will be kept. The data will be kept for 6 years. Data will be presented as mean, standard deviation and percentage. Demographic data will be analyzed using student t test and Chi-Sq as appropriate.

6. Data and Safety Monitoring

Not applicable

7. Reporting Results

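### Objective 3 claims a reduction in anxiety, but a single anonymous survey after delivery can yield only recalled, perceived relief

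*Protocol*

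**What the plan says.** Objective 3 in section 1.1 reads "To determine if the education provided is helpful in reducing maternal anxiety". Section 1.2 states the hypothesis that written material "will improve maternal satisfaction and lessen anxiety in regard to labor". Section 3.3 expects 100 completed surveys to settle whether the literature works as a means of lowering anxiety.

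The outcome comes from one form. Section 4.2 says "After delivery, patients will be asked to complete a questionnaire addressing their thoughts about the pamphlets and their overall satisfaction with their labor analgesia". That sentence does not name anxiety. The one after it does: the analysis is to bear, among other things, "on maternal choice of analgesia modality, and on maternal anxiety regarding their labor analgesia plan".

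The timing is fixed in several places:

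- Section 3.1: "The study will end following delivery when the subject completes the survey on the post-partum unit on F Green".
- Section 3.5.1, first inclusion criterion: "Postpartum women ages 18 and older".
- Section 3.5.4: "The consent letter will be presented to each patient while in the post-partum unit".
- Section 3.6: chart review does not apply.
- Section 5: "The survey is anonymous. No link to the personal health identifiers and data will be kept".

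Sections 3 and 3.1 describe two earlier contacts, in the clinic and on admission to Labor and Delivery. Both deliver the material, and the second adds a discussion of 15-20 minutes. Neither is described as collecting data.

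**The concern.** The anxiety at issue belongs to the time before and during labor. Section 1.2 ties it to labor and section 4.2 to the analgesia plan; by the time of the survey both are over. A woman who is then asked about that anxiety has to reconstruct it, and she already knows whether her analgesia worked and how the birth went.

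Experiences will differ within the sample. Cesarean delivery after a trial of labor is eligible (section 3.5.1, criterion 6), and overall satisfaction with analgesia is asked on the same form. A good or bad experience can carry over into how earlier anxiety, and the pamphlet's part in easing it, are remembered.

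What is at stake is the claim. Followed exactly, the protocol yields a remembered perception, while its objective, hypothesis and sample-size statement promise a finding about anxiety itself.

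**Working it through.** No formula applies to the main point, and there is no planned figure to reproduce: the target of 100 surveys comes with no effect size, standard deviation, power or significance level. The check is to go through every contact in the protocol and ask whether anxiety is measured there.

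| Contact | What happens | Anxiety assessments |
|---|---|---|
| Antenatal clinic (3, 3.5.3) | Pamphlet made available | 0 |
| Admission to Labor and Delivery (3, 3.1) | Pamphlet again, discussion | 0 |
| Labor and delivery | No data collection described | 0 |
| Post-partum unit (3.1, 3.5.4, 4.2) | Consent letter, then survey | 1, retrospective |

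**Could an earlier value come from elsewhere?** No. Chart review is ruled out (3.6), consent is first sought after delivery (3.5.4), and an anonymous form without a link (5) could not be joined to an earlier record.

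**Could the wording of the questionnaire or a separate analysis plan repair it?** The questionnaire is not shown. Whatever its items say, a single form completed after delivery cannot be a rating made at the time. An analysis plan works on the data the protocol collects and cannot add a measurement point.

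**Would a larger sample help?** It would reduce random error. It would not remove an influence of the birth experience on recall.

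**How large is that influence?** The documents give no figure and none can be derived from them. That recall is open to coloring is a methodological inference, not something the protocol reports.

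**What could a breakdown by birth experience show?** For a percentage near 50%, the 95% half-width is 1.96 × √(0.5 × 0.5 / n) = 0.98 / √n. Group sizes below 100 are assumptions.

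- All 100 surveys: 0.98 / √100 = 9.8 points.
- A group of 50: 0.98 / √50 = 13.9 points.
- A group of 20: 0.98 / √20 = 21.9 points.

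A breakdown can therefore reveal a large gradient, but not a small one.

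**The case against.** The best defense is that this is a perception survey. Objective 3 asks whether education is helpful, section 4.2 speaks of women's thoughts about the pamphlets, and section 4.4 says the data will help the investigators learn what their patients need. Perceived helpfulness can be reported only after exposure, so asking on the post-partum unit is defensible. This stands, and it is why the remedy is mainly one of wording. It does not rescue the hypothesis in section 1.2 or the statement in section 3.3, which speak of lessening or reducing anxiety.

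A reader might go further and infer that relief after birth, which comes with or without education, would by itself produce a favorable result, so that objective 3 is left wholly unanswered. The documents do not support tying that to the timing of the survey. It is mainly a consequence of having no comparator: in a randomized comparison surveyed at the same time, natural relief and the mix of birth experiences would be expected to balance between arms. What timing adds is less precise recall, and possible coloring by the birth experience, including through any effect of education on that experience. The relief argument also bites hardest if women rate their current anxiety, and the items are not available to show that they do.

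Two exclusions in section 3.5.2 narrow the range of experience: precipitous labor or late presentation, and fetal distress, where either ruled out an analgesic intervention. This reduces the contrast between good and poor experiences but does not remove it, since cesarean after a trial of labor stays eligible.

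**Conclusion.** The point holds as a mismatch between claim and measurement. The protocol plans no anxiety assessment before delivery and one after it, so it can support a statement about perceived anxiety reduction as recalled after delivery, and nothing stronger about timing. The size of any recall bias is unknown. A numerical illustration would need invented response rates, and comparing two hypothetical mixes of birth experience would not show a bias in this single-group study.

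The conclusion assumes that the contacts described in the protocol are the only ones at which data are collected. It does not depend on the questionnaire's wording. It does not show that the education had no effect or that a favorable answer would be false.

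**What to change.** 1. Restate objective 3, the hypothesis in section 1.2 and the claim in section 3.3 as *perceived anxiety reduction as recalled after delivery*. Use one description of the anxiety meant, since sections 1.2 and 4.2 differ on whether it concerns labor or the analgesia plan.
2. Put mode of delivery and adequacy of analgesia on the existing anonymous form, unless it already asks for them, and report the recalled-anxiety answers by each. With no chart review and no link, the form is the only place these can come from. Treat the breakdown as descriptive: education may itself affect how analgesia goes, so it is not a correction for bias.

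The cost is a protocol and form amendment, two more items on a 10-15 minute survey, imprecise subgroups within 100 surveys, and a more modest claim. No visit or linkage is added.

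An anxiety rating before and after the admission discussion may look like a better remedy, but it should not be the basis for objective 3. It would capture only the change across that 15-20 minute talk and miss the pamphlet given antenatally. It would also be open to the effects of labor pain and would be collected before consent is sought. A card kept through labor could be lost more often after difficult births.

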3.4 Subject Selection and Enrollment Considerations

RUTGERS APPROVED

Protocol Version 1.0 - 04/21/15

IRB ID: Pro20150001531

Approval Date: 4/30/2015

Expiration Date:

Add protocol title
PI name

All comers to the antenatal clinic and labor and delivery unit will receive the same educational information. Those women who are not English or Spanish speaking will not be provided with the written educational material and information letter.

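### The protocol claims an effect of education on choice of modality, but a single survey after delivery, with no earlier record and no comparison group, cannot separate the pamphlet from the course of labor

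*Protocol*

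**What the plan says.** The second objective in Section 1.1 is "To determine if the education material provided is helpful to patients in choosing a preference for a particular analgesia modality". Section 4.2 goes further and speaks of the effect of the materials "on maternal choice of analgesia modality, and on maternal anxiety regarding their labor analgesia plan".

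On measurement, Section 4.2 states: "After delivery, patients will be asked to complete a questionnaire addressing their thoughts about the pamphlets and their overall satisfaction with their labor analgesia". Section 3.1 places the end of the study at the same point: "The study will end following delivery when the subject completes the survey on the post-partum unit on F Green". Section 3.6 marks chart review as not applicable. Section 5 makes the survey anonymous, with no link to identifiers.

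On exposure, Section 3.4 says "All comers to the antenatal clinic and labor and delivery unit will receive the same educational information", and Section 3.5.1 admits "Patients who received our informational pamphlet while pregnant or in labor". Sections 3 and 3.1 add a discussion with the anesthesia provider at arrival.

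The background in Section 2 cites two rates of change: "50% of patients planning for analgesia-free labor request neuraxial analgesia after experiencing labor pain", and "greater than 10% of obese women changed their preference toward epidural analgesia following antenatal consultation".

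**The concern.** An effect on choice is a difference between what a woman would have chosen without the material and what she chose with it. To approach that, a study needs a preference recorded before the other influences act, or a group without the material, and preferably both. The protocol describes neither. By the time of the survey a woman may have read the pamphlet once or twice, talked with the anesthesia provider, gone through labor and received some form of analgesia.

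The background names one of these influences as a common occasion for changing plan, and the only measurement is then placed after it. If the survey results are reported as an effect on choice, changes that arose during labor may be credited to the pamphlet. Conversely, a preference that the pamphlet formed but labor later displaced may go unseen. No later analysis plan can repair this, because it cannot recover a time point that was never recorded.

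**Working it through.** **Step 1: the claim against the data.**

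| Needed to separate education from labor | What the protocol provides |
|---|---|
| Preference before the pamphlet | No record described |
| Preference after reading, before labor | No record described |
| Modality received, from an independent source | Chart review not applicable (3.6) |
| A way to match an earlier record to the survey | Anonymous, no link to identifiers (5) |
| A group without the material | None; everyone gets the same information (3.4) |
| Education clearly ahead of labor | Not assured; a first pamphlet in labor is eligible (3.5.1) |

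**Step 2: the plan's own figure.** Section 3.3 sets 100 completed surveys. It cannot be reproduced, because no error rate, power, effect size or event rate is given. The point does not depend on it.

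**Step 3: how large could labor-related switching be?** Inputs:
- N = 100 surveys (Section 3.3);
- r = 0.50, the cited rate of requesting neuraxial analgesia among women who planned none (Section 2);
- s = share of women who plan to labor without analgesia. The protocol does not give it, so it is assumed to lie between 10% and 50%.

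Expected switches with no education effect = N × s × r:
- s = 10%: 100 × 0.10 × 0.50 = 5
- s = 20%: 100 × 0.20 × 0.50 = 10
- s = 30%: 100 × 0.30 × 0.50 = 15
- s = 50%: 100 × 0.50 × 0.50 = 25

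**Step 4: would more surveys help?** The 95% half-width for a proportion p is 1.96 × √(p(1 − p)/100):
- p = 0.05: 0.043
- p = 0.10: 0.059
- p = 0.15: 0.070
- p = 0.25: 0.085

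A larger N narrows these intervals of about 4 to 8 percentage points. It does not split the proportion into a part due to education and a part due to labor.

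**The case against.** The strongest reply is that the protocol nowhere defines the outcome as modality received or as a count of switches. Section 4.2 describes a questionnaire about opinions of the pamphlet and satisfaction. Section 5 plans means, standard deviations and percentages, and names tests for demographic data only. The questionnaire items are not shown and may already ask about the earlier plan and the reason for changing it. This stands in part: it cannot be said that the items are absent. But such answers would be given after labor and without a comparator, so they would yield self-attribution, not the effect that Section 4.2 names.

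Three stronger readings are tempting, and the protocol does not support them.
- *Labor pain alone causes half of these women to change.* The background places the request after the pain and does not state the cause. The causal reading is natural, but it is an inference.
- *The second objective cannot be answered.* It asks whether the material helps women choose, and sets no time for it. Perceived helpfulness can be asked after birth and reported as a percentage. Only the wording about an effect goes too far.
- *Labor-related switching equals or exceeds the education effect sought.* The protocol states no target effect. The cited shift of just over 10% is a change of preference among obese women after a consultation, whereas the 50% concerns requests among women planning no analgesia. At an assumed share of 10% the result is 5 per 100, below that shift. The comparison depends on the share chosen and mixes populations.

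It is also fair to say that Section 3.5.2 excludes women with contraindicated options and those in whom precipitous labor, late presentation or fetal distress precluded an analgesic intervention. That removes some routes by which labor could displace a preference. It does not remove labor pain or the provider discussion.

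**Conclusion.** The point holds in a limited form. As written, the plan cannot separate an effect of the pamphlet on choice of modality from the course of labor or from the arrival discussion. The cause is the combination of one post-delivery measurement, no earlier linkable record and no comparison group; labor-related switching is one consequence of it.

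The illustrative size is 5 to 25 switches per 100 women with no education effect. This rests on an assumed 10% to 50% share planning to labor without analgesia, and on the cited 50% rate applying to this clinic's population. It shows an order of magnitude only, and the conclusion does not depend on it. The change should be made: a stated focus of the analysis is affected and the remedy is cheap, though the descriptive aim of the survey remains achievable.

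**What to change.** 1. **Survey items.** Make sure the post-partum questionnaire asks separately for: the plan before the pamphlet; the plan after reading it; the modality received; the main reason for any change (pamphlet, discussion, labor pain, medical reason); and whether the pamphlet was first received antenatally or in labor. Allow none and undecided as answers to the two plan items.
2. **Optional card.** If the IRB agrees, add an unnamed preference card when the pamphlet is handed out at arrival. The woman notes whether she is already in pain, keeps the card, and attaches it to the survey if she takes part. Anonymity is preserved.
3. **Reporting.** Report the change from before to after reading, and the modality received, descriptively.
4. **Wording.** Restate the Section 4.2 outcome as perceived helpfulness and self-reported change in preference, not as a causal effect.

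The cost is a few short survey items and, if adopted, one card at an existing contact. The card needs an IRB amendment, because Section 3.5.4 seeks agreement only on the post-partum unit. The limits remain: the plans reported on the survey are recalled after labor, some cards will be missing, and women already in pain at arrival are not measured ahead of it. Without a comparator, a change still cannot be firmly attributed to education.

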4.3 Risk of Harm

The investigators are not aware of any risk to subjects participating in this study.

4.4 Potential for Benefit

The potential benefit maybe that the subject is less anxious about the labor and delivery experience. The information gleaned from this data will be helpful to the investigators in regard to determining the needs of the patient population that is served.

5. Data Handling and Statistical Analysis

The paper survey will be inputted to an excel spread sheet in a password protected computer. This computer is located in the research office in the anesthesiology department. This data will only be accessible to members of the study team. The survey is anonymous. No link to the personal health identifiers and data will be kept. The data will be kept for 6 years. Data will be presented as mean, standard deviation and percentage. Demographic data will be analyzed using student t test and Chi-Sq as appropriate.

6. Data and Safety Monitoring

Not applicable

7. Reporting Results

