3.3 Sample Size Justification

We aim for the completion of 100 surveys which will believe will provide us with information to establish as to whether or not this written literature is an effective method in reducing anxiety and improving patient satisfaction.

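### Section 5 puts its only named tests on demographics without naming groups and gives the outcomes descriptive summaries only, so it cannot support the effect claims in Sections 1.2 and 3.3

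*Protocol*

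**What the plan says.** Section 5 of the protocol contains the whole analysis statement, in two sentences. The first covers the data in general: "Data will be presented as mean, standard deviation and percentage". The second names the tests: "Demographic data will be analyzed using student t test and Chi-Sq as appropriate".

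Four other places bear on what those tests could compare:
- Section 3.4: "All comers to the antenatal clinic and labor and delivery unit will receive the same educational information".
- Section 3.5.1 makes exposure a condition of entry: "Patients who received our informational pamphlet while pregnant or in labor".
- Section 4.1, headed "4.1 Independent Variables or Interventions", is answered as not applicable.
- Sections 3.1 and 4.2 place the questionnaire once, after delivery. No baseline measurement is described.

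The conclusions sought are about effect. Section 1.2 hypothesises that "providing written material regarding labor analgesia options will improve maternal satisfaction and lessen anxiety in regard to labor". Section 3.3 says "We aim for the completion of 100 surveys" and expects these to settle whether the literature reduces anxiety and improves satisfaction. Objective 2 in Section 1.1 is different in kind: it asks whether the material helped women choose a modality, which they can be asked directly.

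**The concern.** A t test or chi-square test on demographics normally compares groups. The protocol names no groups, so a reader cannot tell what is being tested. If subsets were picked once the data were in, the p-values would concern who the women are. They would not show whether the pamphlet changed anxiety or satisfaction. The outcomes in the hypothesis have no inferential method attached.

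At stake is what the report may claim. Followed as written, Section 5 would produce tests that do not bear on the hypothesis, beside outcome percentages that could be read as evidence that the pamphlet worked.

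**Working it through.** **1. Claims set against methods**

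| Claim | Where | Method in Section 5 | Supported? |
|---|---|---|---|
| Material improves satisfaction | 1.2, 3.3 | Mean, SD, percentage | No: no comparator or baseline |
| Material lessens anxiety | 1.2, 3.3 (also 1.1, objective 3) | Mean, SD, percentage | No: same reason |
| Material helped women choose a modality | 1.1, objective 2 | Percentage | Yes, as description |
| None stated | – | t and chi-square on demographics | Tests answer no stated question |

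**2. Can groups be found elsewhere in the protocol?** There is no unexposed group, because Section 3.5.1 admits only women who received the pamphlet. Subsets do exist: receipt during pregnancy or in labor, and English or Spanish. Neither is named as a comparison.

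**3. The plan's own figure.** The 100 surveys in Section 3.3 cannot be reproduced. The protocol gives no significance level, power, effect size, SD or precision target. For orientation only, a 95% interval of ±10 points around 50% needs 1.96² × 0.25 / 0.10² = 96.04 women, which is close to 100. Nothing shows that the figure was reached that way.

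**4. Precision of a one-group description.** Inputs: n = 100 (Section 3.3); the 95% level is assumed.

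For a percentage, the exact (Clopper-Pearson) limits for x of n are the 2.5% quantile of Beta(x, n − x + 1) and the 97.5% quantile of Beta(x + 1, n − x):

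| Favourable answers | Exact 95% limits |
|---|---|
| 50 of 100 | 39.8% to 60.2% |
| 70 of 100 | 60.0% to 78.8% |
| 80 of 100 | 70.8% to 87.3% |
| 90 of 100 | 82.4% to 95.1% |

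The normal approximation agrees at 50%: 1.96 × √(0.5 × 0.5 / 100) = 0.098, or 9.8 points.

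For a mean, the half-width is t(0.975, 99 df) × SD / √100 = 1.984 × SD / 10 = 0.198 SD.

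**5. If a subset comparison were named instead.** Assume a two-sided 5% level, 80% power and a continuous outcome. The detectable standardised difference is (1.960 + 0.842) × √(1/n₁ + 1/n₂):

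| Split of 100 | Detectable difference (SD) |
|---|---|
| 50/50 | 0.56 |
| 70/30 | 0.61 |
| 80/20 | 0.70 |
| 90/10 | 0.93 |

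The protocol does not predict the split. A comparison by time of receipt would also concern timing, and without randomisation. It would not compare pamphlet with no pamphlet.

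**The case against.** The strongest reply has four parts.

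- **Intervals and outcome methods often sit in a SAP.** This stands. A SAP may exist, and Section 5 does not rule intervals out, so their absence alone is no finding. An interval can also be worked out from a percentage and its denominator. But the protocol itself commits its named tests to demographics, and a SAP would have to correct that sentence.
- **Usable subsets exist.** This stands in part. That the tests are two-sample is an inference from their names, and comparing demographics between subsets is conventional description. The defect is that no grouping is named; it is not that none is possible.
- **The root problem is the design.** This stands. One group surveyed once cannot show an effect under any choice of test, so adding intervals would not rescue the hypothesis. The repair must therefore reach Sections 1.2 and 3.3 as well as Section 5.
- **The study is a low-risk anonymous survey.** True, but that does not make the effect claim supportable.

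A reader might infer that Section 5 can support none of the study's conclusions. The documents do not bear that out: objective 2 can be answered with percentages. A reader might also want a rule that a majority claim needs a lower limit above 50%. The protocol sets no such criterion, and the questionnaire items and their response formats are not shown, so no threshold of that kind is used here.

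**Conclusion.** The point holds in this limited form. Section 5 assigns its only named tests to demographics without naming groups, and plans descriptive summaries for the rest. It therefore cannot support the claims of better satisfaction and less anxiety in Sections 1.2 and 3.3. It can support a description of how women judged the material.

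That description would be moderately precise: about ±10 points for a percentage near 50%, narrower towards the extremes, and about ±0.2 SD for a mean. These sizes assume all 100 surveys are completed, each item is answered by everyone, and a 95% level is used. They measure sampling uncertainty only and do not size any effect of the pamphlet. The mismatch between tests and claims rests on the protocol's text alone and does not depend on these assumptions.

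**What to change.** **Section 5, tests.** Choose one:
- delete the t and chi-square tests and describe demographics only; or
- name in advance the groups compared, for example pamphlet received in clinic versus in labor, and apply the tests to the questionnaire outcomes.

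The second route works only if the questionnaire records group membership, because the survey is anonymous and unlinked. Its results should be presented as a non-randomised comparison of timing.

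**Section 5, outcomes.** State that each questionnaire outcome is reported with its denominator and a 95% confidence interval: exact for percentages, t-based for means.

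**Sections 1.2 and 3.3.** Restate the hypothesis and the sample-size statement as descriptive, in terms of women's reported views of the pamphlet. The effect wording in the Section 1 aim and in objective 3 of Section 1.1 should follow.

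**Cost.** The descriptive route takes a few sentences and no additional data. The downside is a less definite conclusion: the report shows its uncertainty and no longer claims that the pamphlet reduced anxiety or raised satisfaction.
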